9.6 Exposure and Treatment Compliance

9.6.1 General Considerations

Duration of treatment (days) is defined as the number of days from first exposure to the day of last exposure (both inclusive). Tabulations will be produced for the mITT analysis set.

9.6.2 Controlled Ovarian Stimulation (Fresh Cycle)

IMP

Exposure to gonadotropins, including total dose, duration of stimulation and number of dose adjustments is covered by a secondary endpoint (section 9.7.3.19).

NIMPs

Exposure to GnRH antagonist will be summarized as the total dose administered (µg) and duration of treatment (days).

Exposure to drug used for triggering of final follicular maturation, i.e. hCG or GnRH agonist, is covered by a secondary endpoint (section 9.7.3.8).

Exposure to progesterone will be summarized as the total dose administered (mg) and duration of treatment (days).

Date: 25 Apr 2018 E-Study Protocol-22377; Ver. 1.0 Supersedes: None Page 127 of 159

9.6.3 Cryopreserved Cycles

In the programmed cryopreserved cycles, exposure to estradiol will be summarized by cycle as the total dose administered (mg) and duration of treatment (days), and exposure to IM progesterone will be summarized by cycle as the total dose administered (mg) and duration of treatment (days).

In the natural cryopreserved cycles, exposure to vaginal progesterone will be summarized by cycle as the total dose administered (mg) and duration of treatment (days).

9.6.4 Treatment Compliance

Non-compliance to IMP is expected to be limited and will be presented in listings. Similarly, listings will be prepared for subjects with deviations in the NIMP schedules for the fresh and cryopreserved cycles.

9.7 Efficacy Endpoints Assessments

9.7.1 General Considerations

Primary Endpoint and Secondary Efficacy Endpoints

Upon achieving statistical significance about the primary endpoint at the 0.05 alpha level, the cumulative live birth rate will be formally tested at the 0.05 alpha level for inferential conclusions.

The secondary endpoints related to pregnancy and implantation parameters are considered supportive of the primary endpoint (cumulative ongoing pregnancy rate). The secondary efficacy endpoints related to ovarian response and embryo development parameters are intended to provide additional characterization of FE 999049.

Analysis and Presentation of Primary and Secondary Efficacy Endpoints

Summary tables and treatment comparisons for the primary endpoint will be presented for both the mITT and PP analysis sets. In case that the mITT and ITT analysis sets are not identical (i.e. at least one subject is randomized but not exposed) the summary tables and treatment comparisons will also be presented for the ITT analysis set. As applicable for the secondary endpoints, summary tables and treatment comparisons may be presented for the mITT and PP analysis sets.

All tabulations will be presented by treatment group. Continuous variables will be presented with number of subjects, mean, standard deviation, median, inter-quartile range, minimum, and maximum. Categorical variables will be presented with number and percentage of subjects within each specific category.

Date: 25 Apr 2018 E-Study Protocol-22377; Ver. 1.0 Supersedes: None Page 128 of 159

All statistical tests will be performed using a two-sided test at a 5% significance level. Treatment differences will (where appropriate) be presented with 95% confidence intervals and p-values corresponding to the statistical test of the hypothesis of 'equal effect' against the alternative of 'different effect'.

Visual displays will be produced as appropriate. All primary and secondary efficacy endpoints will be listed. Listings will only be produced for the mITT.

Multiplicity

In order to handle the formal testing procedures for the primary endpoint of cumulative ongoing pregnancy rate and the key post-trial endpoint of cumulative live birth rate, the overall type-I error will be controlled by the use of a hierarchical inferential approach. Statistical significance of the primary endpoint at the 0.05 alpha level is required before drawing inferential conclusions about the key post-trial endpoint of the cumulative live birth rate. This fixed hierarchical approach will ensure a strong control of the overall type-I error rate at the 0.05 level.

All additional analyses of the primary endpoint and secondary efficacy endpoints are considered as supportive. Adjustments for multiplicity will therefore not be applied.

Missing Data

Missing observations for the primary endpoint of cumulative ongoing pregnancy rate will be imputed as 'negative' irrespective of the reason why data are not recorded. Similarly, for other pregnancy endpoints (β hCG, clinical pregnancy and vital pregnancy) missing data will be imputed as 'negative' with the exception of a later observation in that cycle confirming that an earlier missing observation was in fact 'positive', e.g. in case of a missing β hCG test result and a confirmed clinical pregnancy in the same cycle then the β hCG test result will be imputed as 'positive'.

For subjects with transfer but missing observations on the number of viable fetuses 8-9 weeks after transfer the number of viable fetuses will be imputed as zero irrespective of why data is not recorded. For subjects with transfer but missing information on the number of gestational sacs 5-6 weeks after transfer, the number of gestational sacs will be imputed as the number of viable fetuses 8-9 weeks after transfer.

For subjects with cycle cancellation, the numbers of oocytes retrieved, metaphase II oocytes, fertilized oocytes, and blastocysts on day 5 will be imputed as zero.

Date: 25 Apr 2018 E-Study Protocol-22377; Ver. 1.0 Supersedes: None Page 129 of 159

Missing values will not be imputed for any of the other secondary endpoints, unless otherwise noted.

9.7.2 Primary Endpoint

The hypothesis to be tested for the primary endpoint, cumulative ongoing pregnancy rate, is:

H₀: π_{FE} 999049 – $\pi_{Placebo} \le 0$ against the alternative H_A: π_{FE} 999049 – $\pi_{Placebo} > 0$,

where $\pi_{FE 999049}$ and $\pi_{Placebo}$ denote the cumulative ongoing pregnancy rate after the fresh cycle and cryopreserved cycles in subjects aged 35-42 years treated with FE 999049 or placebo, respectively.

 H_0 will be tested against the alternative H_A by constructing a two-sided 95% confidence interval for the difference in the cumulative ongoing pregnancy rates between the two treatment groups using the traditional Wald interval. If the lower limit of the two-sided 95% confidence interval is greater than 0, the null hypothesis H_0 will be rejected. In the case that the number of pregnancies observed in the placebo group is small (<5), then the one-sided Fisher's exact test will be used.

The primary endpoint will be determined as soon as the subject has achieved an ongoing pregnancy, or when all cryopreserved blastocysts have been exhausted, or after assessment of ongoing pregnancy status in cryopreserved cycles initiated within 12 months from the start of controlled ovarian stimulation.

The efficacy analysis will be based on the mITT analysis set, defined as all subjects who were randomized and received at least one dose of IMP (FE 999049 or placebo).

Sensitivity Analyses

The primary analysis will be repeated for the subjects in the PP analysis set as sensitivity analysis, as well as in the ITT analysis set if the ITT analysis set differs from the mITT analysis set. The outcomes of these analyses are considered supportive.

The primary analyses described above will be repeated restricted to subjects with oocytes retrieved and to subjects undergoing blastocyst transfer.

Missing data for the primary endpoint is expected to be limited due to the trial design, but may occur if the subject is lost to follow-up before ongoing pregnancy is assessed. If one or more such subjects have a positive pregnancy test result (β hCG test, clinical pregnancy or vital pregnancy) prior to lost to follow-up, the impact of imputing the ongoing pregnancy will be investigated in a sensitivity analysis.

Date: 25 Apr 2018 E-Study Protocol-22377; Ver. 1.0 Supersedes: None Page 130 of 159

Subgroup Displays

The primary endpoint will also be displayed by the following subgroups:

- Primary reason for infertility (unexplained infertility, tubal infertility, male factor, endometriosis stage I/II, other)
- Method of insemination (IVF, ICSI, IVF/ICSI)
- Age (35-37, 38-40, 41-42 years)
- Body weight (≤ 75 , >75 kg)
- AMH on stimulation day 1 ($<7.5, 7.5 < 15, 15 < 25, \ge 25 \text{ pmol/L}$)
- Center

For each subgroup factor, descriptive statistics for the cumulative ongoing pregnancy rate will be presented by subgroup level and treatment group. These subgroup displays will be prepared for the mITT and PP analysis sets.

9.7.3 Secondary Efficacy Endpoints

Secondary efficacy endpoints will be analyzed based on the mITT analysis set. As specified below, for selected endpoints, analyses will be repeated on the PP analysis set.

9.7.3.1 Ongoing Pregnancy Rate

The ongoing pregnancy rate will be calculated for the fresh cycle, for each cryopreserved cycle, and for cryopreserved cycles cumulatively based on both the total number of subjects in the treatment group and the total number of subjects who started the respective cycle. For subjects with an ongoing pregnancy, the number of intrauterine viable fetuses will be tabulated. Analyses similar to that used for the primary endpoint will be applied as applicable and will be applied to both the mITT and PP analysis sets.

9.7.3.2 Time to Ongoing Pregnancy

For subjects who achieve ongoing pregnancy following a fresh or cryopreserved transfer, time to ongoing pregnancy across the fresh and cryopreserved cycles will be calculated as the number of days from the start of controlled ovarian stimulation to the visit confirming ongoing pregnancy, as well as the number of cycles until ongoing pregnancy is achieved. Descriptive statistics will be presented by treatment group, and will be applied to both the mITT and PP analysis sets.

Trial Code: 000002 Date: 25 Apr 2018 E-Study Protocol-22377; Ver. 1.0

> Supersedes: None Page 131 of 159

9.7.3.3 Ongoing Implantation Rate

The ongoing implantation rate will be calculated for the fresh cycle, for each cryopreserved cycle, cumulatively for the cryopreserved cycles, and cumulatively across the fresh and cryopreserved cycles for subjects with at least one transferred blastocyst in the applicable cycles. For subjects where the number of viable fetuses 8-9 weeks after transfer is greater than the number of blastocysts transferred, the number of viable fetuses will be set to the number of blastocyst transferred in the analysis. Descriptive statistics will be presented by treatment group and the two treatment groups will be compared using the nonparametric Wilcoxon rank-sum test as applicable. The analyses will be applied to both the mITT and PP analysis sets.

9.7.3.4 Clinical Pregnancy Rate

The clinical pregnancy rate will be calculated for the fresh cycle, for each cryopreserved cycle, cumulatively for the cryopreserved cycles, and cumulatively across the fresh and cryopreserved cycles based on both the total number of subjects in the treatment group and the total number of subjects who started the respective cycle. The analyses will be conducted in a similar manner as ongoing pregnancy rate and will be applied to both the mITT and PP analysis sets. For subjects with clinical pregnancy, the type of clinical pregnancy (intrauterine or ectopic) will be tabulated.

9.7.3.5 Vital Pregnancy Rate

The vital pregnancy rate will be calculated and analyzed in a similar manner as ongoing pregnancy rate and will be applied to both the mITT and PP analysis sets.

9.7.3.6 Implantation Rate

The implantation rate will be calculated and analyzed in a similar manner as ongoing implantation rate and will be applied to both the mITT and PP analysis sets.

9.7.3.7 Positive βhCG Rate

The positive βhCG rate will be calculated and analyzed in a similar manner as ongoing pregnancy rate and will be applied to both the mITT and PP analysis sets.

Date: 25 Apr 2018 E-Study Protocol-22377; Ver. 1.0 Supersedes: None Page 132 of 159

9.7.3.8 Triggering of Final Follicular Maturation, Cycle Cancellation and Transfer Cancellation

The proportion of subjects with triggering of final follicular maturation will be tabulated by triggering drug (hCG, GnRH agonist) and in total. The proportion of subjects with cycle cancellation or transfer cancellation in the cycle will also be tabulated, including the reasons.

9.7.3.9 Number and Size of Follicles during Stimulation

The follicle cohort on stimulation day 5 and end-of-stimulation will be summarized by treatment on the follicle level (number of follicles 8-9 mm, 10-11 mm, 12-14 mm, 15-16 mm and \geq 17 mm) and on the subject level (total number of follicles, size of largest follicle, average follicle size, average size of three largest follicles, and number of follicles \geq 8 mm, \geq 10 mm, \geq 12 mm, \geq 15 mm and \geq 17 mm). Continuous data will be compared between treatment groups using Wilcoxon's test. Categorical data will be compared between treatment groups using the chi-square test or Fisher's exact test in case of sparse data. The analyses will be applied to both the mITT and PP analysis sets.

9.7.3.10 Number and Distribution of Oocytes Retrieved

The number of oocytes retrieved will be tabulated including summary statistics. Furthermore, a frequency table with subjects grouped according to number of oocytes retrieved will be prepared using these categories: <4, 4-7, 8-14, 15-19 and ≥20 oocytes. Subjects with cycle cancellation due to poor ovarian response will be included in the <4 oocytes group. Continuous data will be compared between treatment groups using Wilcoxon's test. Categorical data will be compared between treatment groups using the chi-square test or Fisher's exact test in case of sparse data. The analyses will be applied to both the mITT and PP analysis sets.

9.7.3.11 Number of Metaphase II Oocytes

Oocytes undergoing ICSI will have their maturity stage assessed prior to insemination. The number of metaphase II (MII) oocytes per subject will be tabulated including both summary statistics and a frequency table. Furthermore, the percentage of MII oocytes to oocytes retrieved for subjects where all oocytes are inseminated using ICSI will be tabulated. Continuous data will be compared between treatment groups using Wilcoxon's test. Categorical data will be compared between treatment groups using the chi-square test or Fisher's exact test in case of sparse data. The analyses will be applied to both the mITT and PP analysis sets.

Trial Code: 000002 Date: 25 Apr 2018 E-Study Protocol-22377; Ver. 1.0

Supersedes: None Page 133 of 159

9.7.3.12 Number of Fertilized Oocytes and Fertilization Rate

An oocyte is defined as fertilized if it is scored as 2PN at 19h (\pm 2h). The number of fertilized oocytes per subject will be tabulated including both summary statistics and a frequency table. Furthermore, for subjects with oocytes retrieved, the rate of fertilized oocytes to oocytes retrieved (and also the rate of fertilized oocytes to metaphase II oocytes for those inseminated using ICSI) will be tabulated overall and by method of insemination. Continuous data will be compared between treatment groups using Wilcoxon's test as applicable. Categorical data will be compared between treatment groups using the chi-square test or Fisher's exact test in case of sparse data. The analyses will be applied to both the mITT and PP analysis sets.

9.7.3.13 Number and Quality of Blastocysts on Day 5

The number of blastocysts on day 5 including a breakdown in quality scores will be tabulated including both summary statistics and frequency tables. Tables will be produced overall and by method of insemination. The percentage of subjects with at least one good-quality blastocyst, i.e. of grade 3BB or aboveⁱ, will be reported. Further, for subjects with oocytes retrieved, the rate of blastocysts to oocytes retrieved will be summarized overall and by quality score. Continuous data will be compared between treatment groups using Wilcoxon's test. Categorical data will be compared between treatment groups using the chi-square test or Fisher's exact test in case of sparse data. The analyses will be applied to both the mITT and PP analysis sets.

9.7.3.14 Endometrial Thickness and Echogenicity Pattern

Endometrial thickness on stimulation day 5 and at end-of-stimulation will be tabulated including summary statistics. Endometrial echogenicity pattern on stimulation day 5 and at end-of-stimulation will be tabulated. Continuous data will be compared between treatment groups using Wilcoxon's test. Categorical data will be compared between treatment groups using the chi-square test or Fisher's exact test in case of sparse data. The analyses will be applied to both the mITT and PP analysis sets.

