4.1.2 Exclusion Criteria

Subjects meeting any of the criteria listed below will not be eligible for participation in this trial.

- 1. More than one previous controlled ovarian stimulation cycle for IVF/ICSI.
- 2. Known endometriosis stage III-IV (defined by the revised ASRM classification, 2012²⁸).
- 3. Known history of anovulation.
- 4. One or more follicles ≥10 mm (including cysts) observed on the transvaginal ultrasound prior to randomization on stimulation day 1.
- 5. Known history of recurrent miscarriage (defined as three consecutive losses after ultrasound confirmation of pregnancy [excl. ectopic pregnancy] and before week 24 of pregnancy).
- 6. Known abnormal karyotype of subject or of her partner / sperm donor, as applicable, depending on source of sperm used for insemination in this trial. In case partner sperm will be used and the sperm production is severely impaired (concentration <1 million/mL), normal karyotype, including no Y-chromosome microdeletion, must be documented.
- 7. Any known clinically significant systemic disease (e.g. insulin-dependent diabetes).
- 8. Known inherited or acquired thrombophilia.
- 9. Active arterial or venous thromboembolism or severe thrombophlebitis, or a history of these events.
- 10. Any known endocrine or metabolic abnormalities (pituitary, adrenal, pancreas, liver or kidney) with the exception of pharmacologically controlled sub-clinical hypothyroidism.
- 11. Known tumors of the ovary, breast, uterus, adrenal gland, pituitary or hypothalamus which would contraindicate the use of gonadotropins.
- 12. Known moderate or severe impairment of renal or hepatic function.
- 13. Any abnormal finding of clinical chemistry, hematology, thyroid-stimulating hormone (TSH) or prolactin, or vital signs at screening, which is judged clinically significant by the investigator.
- 14. Currently breast-feeding.
- 15. Undiagnosed vaginal bleeding.
- 16. Known abnormal cervical cytology of clinical significance observed within three years prior to randomization (unless the clinical significance has been resolved).
- 17. Findings at the gynecological examination at screening which preclude gonadotropin stimulation or are associated with a reduced chance of pregnancy, e.g. congenital uterine abnormalities or retained intrauterine device.
- 18. Pregnancy (negative urinary pregnancy tests must be documented at screening and prior to randomization) or contraindication to pregnancy.

E-Study Protocol-22377; Ver. 1.0

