Subjects will attend the stimulation day 1 visit on day 2-3 of their menstrual cycle.

The following must take place prior to randomization:

- Ensure that the subject is still eligible for participation in the trial
- Check those inclusion and exclusion criteria that were not possible during screening
- Body weight
- Urine pregnancy test must be negative
- Transvaginal ultrasound of uterus (endometrial thickness, echogenicity pattern) and ovaries (number and size of follicles, ovarian volume)

If the subject fulfills all inclusion and exclusion criteria, she will proceed to randomization:

• Randomization, i.e. assignment to the lowest available subject number and thereby allocation to either FE 999049 or placebo

The following must take place after randomization but before administration of the first dose of IMP (FE 999049 or placebo):

- Vital signs (systolic blood pressure, diastolic blood pressure, pulse)
- Blood collection for central laboratory analysis of:
 - endocrine parameters (AMH, FSH, LH, estradiol, progesterone, inhibin A and inhibin B)
 - anti-FSH antibodies

Date: 25 Apr 2018 E-Study Protocol-22377; Ver. 1.0 Supersedes: None Page 72 of 159

- Blood collection for future potential genome sequencing (applicable for subjects who have provided a separate informed consent)
- Saliva collection for future potential genome sequencing (applicable for subjects who have provided a separate informed consent)
- Tongue coat collection for future potential microbial profiling (applicable for subjects who have provided a separate informed consent)

Once the above has been completed, the following must be performed:

- Hand out the diary for recording of local tolerability to the subject. The subject must be instructed to assess and record local tolerability after each IMP administration throughout the entire stimulation period. The first evaluation of local tolerability reactions at the injection site is done immediately after the injection of IMP, followed by a second evaluation 30 minutes after injection of IMP and a third evaluation 24 hours after injection of IMP (before the next day's injection of IMP). In case the subject has any concern related to an injection site reaction, the investigator should be contacted for possible further assessment, prior to the next IMP injection.

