9.7.3.18 Circulating Levels of Endocrine Parameters

Blood samples drawn on stimulation day 1, stimulation day 5, end-of-stimulation, and oocyte retrieval will be analyzed for AMH, FSH, LH, estradiol, progesterone, inhibin A and inhibin B. Values below the lower limit of quantification (LLOQ) will be included as LLOQ/2. Values above the upper limit of quantification (ULOQ) will be included as ULOQ.

Each endocrine parameter and the change from baseline for post-baseline measurements will be tabulated for stimulation day 1 (baseline), stimulation day 5, end-of-stimulation and oocyte retrieval. For each parameter the change from baseline will be compared between treatment groups using a lognormal model. In this model change from baseline in log-transformed measurements will be the dependent variable and the linear predictor will include treatment as factor and baseline measurement (log-transformed) as covariate. The estimated treatment difference with 95% confidence interval will be presented on the original scale of measurement (i.e. exp-transformation applied to the log-transformed measurement) and accompanied by the p-value for test of no treatment difference.

Further, a population pharmacokinetic model will be used for evaluating the effects of subject characteristics on FSH concentrations and for assessing the variability in exposure. The modelling analysis will be described in a modelling analysis plan and the results reported separately from the clinical trial report.

Date: 25 Apr 2018 E-Study Protocol-22377; Ver. 1.0 Supersedes: None Page 135 of 159

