7.10 Endocrine Parameters

At the screening visit, blood samples will be collected for analysis of the following endocrine parameters: AMH (pmol/L), TSH (mIU/L) and prolactin (pmol/L). On stimulation day 1, blood samples will be collected for analysis of the following endocrine parameters: AMH (pmol/L), FSH (IU/L), LH (IU/L), estradiol (pmol/L), progesterone (nmol/L), inhibin A (ng/L) and inhibin B (ng/L). These endocrine parameters at baseline will be tabulated (AMH on stimulation day 1 is considered the baseline value).

In addition, a frequency table will be produced for AMH on stimulation day 1 (<7.5, 7.5-<15, 15-<25, \geq 25 pmol/L).

Values below the lower limit of quantification (LLOQ) will be included as LLOQ/2. Values above the upper limit of quantification (ULOQ) will be included as ULOQ.

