7.13 Follicles

The number of follicles on stimulation day 1 will be summarized and tabulated using the categories 0-4, 5-9 and \geq 10 follicles.

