7.14 Endometrial Thickness

The endometrial thickness (mm) on stimulation day 1 will be summarized and tabulated using the categories ≤ 6 mm, 7-9 mm, ≥ 10 mm.

7.15 **Prior and Concomitant Medication**

Prior and concomitant medication will be will be coded using the World Health Organization (WHO) Drug Reference List. They will be summarized by anatomical therapeutic chemical (ATC) classification 1st level (alphabetically), ATC classification 2nd level (in decreasing order of frequency) and treatment group. These medications will be tabulated separately for:

- 1) Prior medication; i.e. medication taken exclusively prior to treatment (i.e. with stop date/time before date/time of first IMP administration);
- 2) Concomitant medication, i.e. medication taken during the treatment period (i.e. medication that was not stopped before date/time of first IMP administration and not started after the end-of-cycle visit).

Concomitant medication will be presented separately for the fresh cycle and the cryopreserved cycles.

If the timing of the dose of a concomitant medication cannot be established in relation to the administration of IMP, it will be considered as concomitant medication.

Prior and concomitant medication will be listed by treatment group and subject number for the mITT analysis set.

8 Exposure and Treatment Compliance

Tabulations will be produced for the mITT and PP analysis set.

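### Endometrial thickness and total or small-follicle counts are compared without the day 1 value already measured; a baseline-adjusted supportive analysis would be a minor, free gain in precision

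*Protocol*

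**What the plan says.** Protocol 9.7.3.14 (endometrial thickness) specifies: "Continuous data will be compared between treatment groups using Wilcoxon". Protocol 9.7.3.9 (follicles) and 9.7.3.10 (oocytes) name the same test, and SAP 9.4.9, 9.4.10 and 9.4.14 keep it. None of these sections names a covariate, a stratification factor or an estimator of the treatment difference.

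The day 1 values exist. Protocol 6.1.2 (Stimulation Day 1) lists, among the steps before randomization: "Transvaginal ultrasound of uterus (endometrial thickness, echogenicity pattern) and ovaries (number and size of follicles, ovarian volume". The SAP uses these values only descriptively. Section 7.13 reads "The number of follicles on stimulation day 1 will be summarized and tabulated using the categories" given there, and section 7.14 reads "The endometrial thickness (mm) on stimulation day 1 will be summarized and tabulated using the categories" given there. For AMH, SAP 7.10 notes that "AMH on stimulation day 1 is considered the baseline value".

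The endocrine endpoints, sampled at the same day 5 and end-of-stimulation visits, are handled differently. In the log-normal model of Protocol 9.7.3.18 (repeated in SAP 9.4.18), "the linear predictor will include treatment as factor and baseline measurement (log-transformed) as covariate".

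Allocation is 500:50 (Protocol 9.1). Randomization is blocked, and no stratification factor is described (Protocol 4.2.2). Protocol 9.7.1 and SAP 9.2.1 class the secondary efficacy analyses as supportive.

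**The concern.** Precision for any between-arm contrast here is limited by 50 placebo women. When the outcome measure has also been taken before randomization, conditioning on it removes the part of the between-woman variation that the baseline predicts. It also removes the effect of a chance baseline difference, which an unstratified 10:1 design does not prevent. The plan does this for hormones but not for endometrial thickness or follicle number, and it gives no reason.

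At stake is the width of the interval and the power for endpoints where the effect may be modest, endometrial thickness above all. Characterizing ovarian response, including follicular development, is a stated secondary objective (Protocol 2.1), so the quality of the follicle estimate has some value. No error in the trial's conclusions is at stake.

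**Working it through.** **The plan's own figure.** The documents state no power or precision for these endpoints. The only efficacy power statements are for the pregnancy and live birth rates. For 30% versus 3% at 500:50, the pooled two-proportion calculation and exact enumeration of the planned rule (one-sided Fisher test if there are fewer than 5 placebo pregnancies, otherwise Wald) both give over 99.99%, in line with the stated figure of at least 99%. Fifty placebo women are ample for that comparison, but it says nothing about endometrial or follicle measures.

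**Inputs.** n = 500 and 50; two-sided 5% (Protocol 9.7.1). The correlation r between the day 1 and later values is assumed to be 0.2 to 0.7, with a similar slope in both arms.

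**Precision in SD units.**

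- Unadjusted SE = √(1/50 + 1/500) = √0.022 = 0.148; half-width = 1.96 × 0.148 = 0.291.
- Adjusted SE = 0.148 × √(1 − r²).
- Effect detectable with 80% power = SE × (1.960 + 0.842).

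| r | variance reduction (r²) | 95% CI half-width (SD) | detectable effect, 80% power (SD) |
|---|---|---|---|
| 0 | 0% | 0.291 | 0.416 |
| 0.2 | 4% | 0.285 | 0.407 |
| 0.3 | 9% | 0.277 | 0.396 |
| 0.5 | 25% | 0.252 | 0.360 |
| 0.7 | 49% | 0.208 | 0.297 |

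Under normality the Wilcoxon test has relative efficiency 0.955, so its detectable effect is 0.416/√0.955 = 0.425 SD.

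**Power at a 0.4 SD difference** (simulated, 3,000 trials per setting, bivariate normal, 500:50). The Wilcoxon test has about 75% throughout. Rank ANCOVA (Quade) has 78% at r = 0.3, 85% at 0.5 and 95% at 0.7. At r = 0.2 the gain is about one percentage point. Null rejection stayed between 4% and 5.5%.

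**Chance imbalance.** Baseline means differ by 1.96 × 0.148 = 0.29 SD or more in 1 trial in 20. At r = 0.5 an imbalance of that size moves the unadjusted difference by 0.5 × 0.29 ≈ 0.15 SD.

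**Which endpoints have a usable baseline.**

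- *Endometrial thickness:* the same measure is taken on day 1.
- *Total and small-follicle counts:* the same measure is taken on day 1 and can vary.
- *Counts of follicles of 10 mm or more:* exclusion criterion 4 bars any such follicle "observed on the transvaginal ultrasound prior to randomization on stimulation day 1". The day 1 value is therefore zero for every eligible woman and can adjust nothing.
- *Oocytes:* there is no day 1 value; AMH is the only candidate covariate. Suppose placebo counts are near zero, which Protocol 3.5.1 (placebo women look like poor responders) and the zero imputation for cancelled cycles in 9.7.1 make plausible but do not prove. Relative to the unadjusted variance σ²/500, a common-slope model has (1 − r²)/500 + r²/50. At r = 0.3 this is (0.00182 + 0.00180)/0.002 = 1.81 times; at r = 0.5 it is (0.0015 + 0.0050)/0.002 = 3.25 times. Arm-specific slopes give (1 − r²)/500 + r²/550, or 0.98 times at r = 0.5. A less extreme simulation (60% to 90% zero counts on placebo) still gave 2.2 to 2.5 times for the common slope at r = 0.5.

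**The case against.** The strongest reply is that nothing here is wrong. Randomization makes the unadjusted comparison valid, chance imbalance is already part of its 5% error rate, and baseline values will be tabulated by arm, so an imbalance will be visible. The Wilcoxon test is a sound choice for skewed, zero-heavy counts. All of this stands.

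The correlation is assumed and may be small. End-of-stimulation is not a fixed time: it falls at triggering or cancellation, up to day 20 (Protocol 6.1.5), so a strong link with day 1 cannot be presumed. At r = 0.1 to 0.2 the variance falls by only 1% to 4%. This stands, and the table therefore starts at a weak correlation.

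A reader might infer that the plan contradicts itself because it adjusts hormones but not ultrasound measures. The documents do not support that. The endocrine analysis models change from baseline, whereas the follicle and endometrial endpoints are defined as values at the visit, and different methods for different endpoints are not a contradiction. The endocrine model shows only that baseline adjustment is already accepted in this plan.

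A reader might also extend the point to oocyte number and every follicle class. The working shows why that fails: the baseline is constant for follicles of 10 mm or more, and a common-slope AMH model could widen the oocyte interval.

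**Conclusion.** The point holds as a minor efficiency improvement for endometrial thickness and for total and small-follicle counts. The potential gain is a 4% to 49% reduction in variance, or a half-width of 0.285 to 0.208 SD instead of 0.291 SD. It rests on an assumed correlation of 0.2 to 0.7 and on similar slopes in the two arms; the documents supply neither. The power figures also assume normal data and a constant shift.

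It would be wrong to conclude that the planned tests are biased or that a trial conclusion is at risk. Type I error is held at 5%, and these endpoints lie outside the hierarchy of cumulative ongoing pregnancy followed by cumulative live birth.

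**What to change.** In Protocol 9.7.3.9 and 9.7.3.14 and SAP 9.4.9 and 9.4.14, for endometrial thickness and total and small-follicle (under 10 mm) counts only:

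1. Add a rank analysis of covariance (Quade) with the stimulation day 1 value of the same measure as covariate.
2. Add a baseline-adjusted mean difference with a 95% CI from robust standard errors.
3. Keep the Wilcoxon test alongside.

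Leave counts of follicles of 10 mm or more unadjusted. Leave oocyte number (Protocol 9.7.3.10, SAP 9.4.10) unadjusted, or use a model with arm-specific AMH slopes. List the addition in SAP section 14 and make it before unblinding.

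The cost is a few sentences and a few lines of code, with no new visits or samples. Day 1 thickness and total follicle number are already due to be tabulated. Protocol 7.1.9 describes recording by size class only for day 5 and end-of-stimulation, so confirm that day 1 follicle sizes are in the eCRF before specifying the small-follicle covariate.
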